## Statistical analysis plan JUMPER-study

Participants will be analyzed by intention-to-treat. To test for the effect on the between-group difference in primary outcome (VISA-P score), we will use the Generalized Estimating Equation (GEE) model. Adjustments will be made for the following baseline variables: age, sex, BMI, duration of symptoms and activity level (Cincinnati Sports Activity Scale). The same approach will be used for the following secondary outcomes: VAS score on palpation of the proximal patellar tendon, VAS score in the patellar tendon during single leg decline squat before and after isometric exercises, VAS score during the latest sport activity, VAS score during activities of daily living, muscle force and flexibility of upper and lower leg muscles, vertical jump height and two dimensional video-based analysis of the drop vertical jump test.

Compliance to the exercise therapy and the amount of experienced pain (VAS 0-10) will also be analyzed in a secondary analysis to test for the effect of compliance on the primary outcome using the GEE-model.

This GEE-model will also be used to determine the association between the following variables and the course of symptoms resulting from patellar tendinopathy: the level of passive coping (measured with the Pain Coping Inventory) and presence of a neuropathic pain component (measured with the painDETECT questionnaire).

Fisher's exact test will be performed for the following categorized secondary outcomes: return to desired sport and subjective patient satisfaction, which we will dichotomize, for the following categories (A) return to desired sport at pre-injury level, (B) return to desired sport, but not at pre-injury level, (C) return to sport, but not to desired sport, (D) no return to sport and (A) excellent, (B) good, (C) moderate, (D) poor, respectively. For example, return to desired sport at pre-injury level (1) and other categories as (0) and excellent/good as satisfied (1) and moderate/poor as dissatisfied (0), for return to sport and subjective patient satisfaction respectively.

Missing data will not be imputed to avoid the introduction of biased estimates of treatment effect. We chose this approach because it is likely that missing data will not occur at random. This assumption is based on the facts that patients are not blinded to the allocated therapy and one exercise program is expected to cause significantly more pain than the other exercise program. Therefore, only a sensitivity analysis will be performed if missing data is more than 5%, blinded for the allocated exercise therapy.

We intend to publish results of this study in multiple papers, given the large amount of data derived from this randomized controlled trial.

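### The adjustment list for the primary VISA-P GEE omits baseline VISA-P, and the SAP does not otherwise say how the baseline score enters the model

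*SAP*

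**What the plan says.** The first paragraph of the SAP (section Statistical analysis plan JUMPER-study) names the primary model: "To test for the effect on the between-group difference in primary outcome (VISA-P score), we will use the Generalized Estimating Equation (GEE) model". The next sentence gives its adjustment variables: "Adjustments will be made for the following baseline variables: age, sex, BMI, duration of symptoms and activity level (Cincinnati Sports Activity Scale". These are five variables, and the baseline value of VISA-P is not one of them.

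The paragraph then extends the method: "The same approach will be used for the following secondary outcomes". The natural reading, though not an explicit statement, is that the same list goes with it, so each continuous secondary outcome is also modelled without its own baseline value.

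The third paragraph uses the model once more: "This GEE-model will also be used to determine the association between the following variables and the course of symptoms resulting from patellar tendinopathy". The missing-data paragraph adds that "Missing data will not be imputed to avoid the introduction of biased estimates of treatment effect". Nowhere does the SAP describe baseline VISA-P as a covariate, as one of the repeated responses, or as a value to subtract.

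**The concern.** The baseline value of a repeated score is usually among the strongest predictors of its later values. A list that names five other baseline variables and leaves this one out would, if followed literally, produce a primary model without it. This is not a detail that the SAP merely leaves to the protocol, because the SAP itself chooses the covariates.

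Three things are at stake:

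- The confidence interval for the primary comparison may be wider than it needs to be.
- A chance difference between the arms at baseline moves the estimate.
- Several analyses fit the text and react differently to such an imbalance, so the choice between them could be made after the data are seen.

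**Working it through.** **What the text allows.** Four models fit the wording:

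- (a) Follow-up scores only, with no baseline term.
- (b) Baseline as a response with a free mean per arm. The treatment contrast is then an unconstrained change from baseline.
- (c) Baseline as a response with one mean common to both arms.
- (d) Baseline as a response with only a group main effect.

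**Inputs.** The SAP gives no SD, correlation or number of visits, so there is no figure of its own to reproduce. Everything below is assumed and illustrative:

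- one follow-up visit (except for model (d) below) and complete data;
- baseline-to-follow-up correlation r = 0.3 / 0.5 / 0.7;
- share R² of both scores explained by the five covariates = 0 or 0.20, through one shared linear predictor;
- equal SDs, unless a follow-up/baseline SD ratio s is given.

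The correlation left after the covariates is p = (r − R²)/(1 − R²). For R² = 0, p = r. For R² = 0.20, p = 0.1/0.8, 0.3/0.8, 0.5/0.8 = 0.125 / 0.375 / 0.625.

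**Variance of the treatment contrast, equal SDs.** Relative to follow-up-only = 1, change score is 2(1 − p) and conditioning on baseline is 1 − p². The cut from conditioning is therefore p² against follow-up-only, and 1 − (1 + p)/2 against change score.

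| Comparison | R² | r = 0.3 | r = 0.5 | r = 0.7 |
|---|---|---|---|---|
| against (a) | 0 | 9% | 25% | 49% |
| against (a) | 0.20 | 2% | 14% | 39% |
| against (b) | 0 | 35% | 25% | 15% |
| against (b) | 0.20 | 44% | 31% | 19% |

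**Unequal SDs, R² = 0.** Against change score the cut is 1 − s²(1 − r²)/(1 + s² − 2rs). At s = 1.5 it is 13% / 4% / 0%. At s = 2 it is 4% / 0% / 7%. For example, at s = 2 and r = 0.5: 1 − 4(0.75)/(5 − 2) = 0. The gain vanishes where rs = 1 and is small nearby. The cut against follow-up-only does not depend on s.

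**Chance imbalance, equal SDs.** Suppose a baseline difference d = 0.25 SD remains after the five covariates. The slope of follow-up on that remainder is p, so the shifts are p·d for (a) and −(1 − p)·d for (b).

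| Model | R² | r = 0.3 | r = 0.5 | r = 0.7 |
|---|---|---|---|---|
| (a) | 0 | +0.075 | +0.125 | +0.175 |
| (a) | 0.20 | +0.031 | +0.094 | +0.156 |
| (b) | 0 | −0.175 | −0.125 | −0.075 |
| (b) | 0.20 | −0.219 | −0.156 | −0.094 |

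The two estimates differ by p·d + (1 − p)·d = 0.25 SD in every column, that is, by the whole imbalance.

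**Group main effect only (d).** With an independence working correlation and a constant effect at k follow-ups, the group coefficient averages over one visit without an effect and k visits with it. It estimates k/(k + 1) of the effect: 0.50, 0.67, 0.75, 0.80 for k = 1 to 4.

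**Common baseline mean (c), R² = 0.** With exchangeable correlation and one common scale, the implied baseline coefficient is b = 2rs/(1 + s²), and the cut against (a) is 2br/s − b²/s². At s = 1 this gives the full 9% / 25% / 49%. At s = 2 it gives 6% / 16% / 31%.

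**The case against.** The strongest reply is that nothing has been left out. In a longitudinal GEE the baseline score can be the first response, and then it would not belong in a list of adjustment variables. The use of the same model for the course of symptoms fits that picture. If a common baseline mean is intended as well, adding the covariate gains little or nothing. This stands as a possibility, but the SAP states neither the baseline response nor the constraint. With a free mean per arm, the result is model (b), which reacts to chance imbalance in the way shown above.

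A second reply is that visit times and the primary time point may be in the protocol, which is not at hand. That is accepted, and their absence is not part of this point. The covariate list is the SAP's own decision.

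A third reply is that every size given here is assumed and that the variance cut runs from 0% to 49% depending on the inputs. That also stands: the figures show what could be lost, not what will be.

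A reader might go further and infer that the trial ignores the baseline score, or that its primary estimate will be biased. The document supports neither inference. Silence on how baseline enters does not show that it is ignored. Under randomisation, a follow-up-only model without the covariate is unbiased on average. Only model (d) would distort the size of the effect, and the SAP does not say that it is the model intended.

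**Conclusion.** The point holds as a matter of precision and specification; it does not show that the primary analysis is invalid. The list omits the outcome's own baseline, and nothing else in the SAP settles its role. With similar SDs at both visits, the follow-up-only and change-score contrasts are both less precise than conditioning on baseline. The gain is small against follow-up-only when the correlation is low and the listed covariates already explain much. It is small or nil against change scores when the follow-up SD is well above the baseline SD and rs is near 1. It is little or nil if model (c) is already meant. What does not depend on the assumed correlation is the discretion: models (a) and (b) differ by the full remaining baseline imbalance. The change is worth making before the data are analysed.

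**What to change.** Add baseline VISA-P to the covariate list and use post-baseline scores as the response, provided VISA-P is measured at baseline, which the SAP does not state. For each continuous secondary outcome measured at baseline, add that outcome's own baseline value.

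If baseline is to stay among the responses, the SAP should say so, constrain the arms to a common baseline mean, allow different variances by visit, and take the treatment effect from post-baseline contrasts. This approximates the covariate model but is not identical to it, and it means respecifying the model rather than adding a sentence.

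The covariate version costs one sentence and one degree of freedom per model. Without imputation it also loses participants who have no baseline score, a complete-case cost that the five listed covariates already carry. Against follow-up-only, the break-even missing fraction m solves (1 − p²)/(1 − m) = 1, so m = p²: 9% / 25% / 49% if the covariates explain nothing and 2% / 14% / 39% at the assumed 20%. This holds if the loss of baseline scores is unrelated to outcome. The common-baseline-mean version keeps those participants.

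### The SAP sets out to test the effect of compliance on VISA-P, but compliance is not randomised, so the planned GEE can support only an association

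*SAP*

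**What the plan says.** All the relevant text stands under the SAP's single heading, Statistical analysis plan JUMPER-study.

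- **First paragraph, principle and primary model.** The analysis principle comes first: "Participants will be analyzed by intention-to-treat". The model for the main comparison is then given: "To test for the effect on the between-group difference in primary outcome (VISA-P score), we will use the Generalized Estimating Equation (GEE) model".
- **First paragraph, adjusters.** Five baseline variables are named: "Adjustments will be made for the following baseline variables: age, sex, BMI, duration of symptoms and activity level (Cincinnati Sports Activity Scale"). They are attached to the primary outcome and, through "The same approach will be used for the following secondary outcomes", to a list of secondary outcomes.
- **Second paragraph, compliance.** The aim and the model for compliance are put this way: "in a secondary analysis to test for the effect of compliance on the primary outcome using the GEE-model". The same sentence also names experienced pain, on a 0 to 10 VAS, as something to be analysed. No weighting, instrument, complier estimand or no-unmeasured-confounding assumption is named for this analysis. The role of pain (covariate, second exposure or outcome) is not stated.
- **Third paragraph, other non-randomised variables.** For passive coping and a neuropathic pain component: "This GEE-model will also be used to determine the association between the following variables and the course of symptoms".
- **Missing-data paragraph.** Patients are unblinded and "one exercise program is expected to cause significantly more pain than the other exercise program".

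**The concern.** Randomisation protects the comparison of the two exercise programmes. It does not protect a comparison of patients who trained more with patients who trained less. Compliance arises during follow-up and can be linked to VISA-P in two ways that involve no effect of training: shared causes (severity, pain, early recovery) and reverse causation (the symptom score changes how much the patient trains). The direction is open, since patients doing badly may train less and recovered patients may stop. A GEE deals with correlation between repeated measurements; it does not remove confounding.

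At stake is one secondary conclusion. If the plan is followed as worded, a compliance coefficient may be reported with the same word that the first paragraph uses for the randomised contrast. The SAP also intends several papers, so this result may be read apart from the main comparison.

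**Working it through.** The SAP gives no figure for this analysis, so there is none to reproduce. The check is a reading of the text, followed by an illustration in which **every input is assumed**.

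**1. Text side by side.** The second and third paragraphs use the same model for variables that are not randomised. For coping and neuropathic pain the target is an association; for compliance, which in addition arises after randomisation, it is an effect. Nothing in the SAP justifies the stronger word.

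**2. Shared cause, true compliance effect zero.** Assume compliance shifts 5 percentage points per SD of latent severity, VISA-P has SD 15 and loads 0.5 on severity, and residual compliance SD is 20. Then

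slope = covariance / variance = (5 × 0.5 × 15) / (5² + 20²) = 37.5 / 425 = 0.088 per point, or 0.88 VISA-P points per 10 percentage points.

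If better patients train less, the sign reverses. A simulation over a wider set of assumptions gave 0.72 to 2.73 in absolute value without pain in the model and 0.58 to 1.12 with it. Including pain removed the bias (-0.02 to 0.03) only where compliance depended on pain alone.

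**3. Chance of a false finding.** In a separate simulation (two visits, VISA-P SD 17, two-sided 5% level, 600 runs) one factor correlates rc with compliance and ry with VISA-P. The expected false slope per SD of compliance is rc × ry × 17.

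| rc, ry | Formula | Simulated slope | Rejected, 40 per arm | Rejected, 80 per arm |
|---|---|---|---|---|
| 0, 0 | 0 | about 0 | 5.3% | 5.5% |
| 0.3, 0.3 | 1.53 | 1.50 to 1.53 | 19% | 27% |
| 0.5, 0.5 | 4.25 | 4.18 to 4.19 | 71% | 96% |

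A larger sample makes the false finding more likely.

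**4. Reverse causation and timing of compliance.** Assume compliance from the second interval on shifts 5 points per SD of the previous VISA-P. VISA-P has SD 15 and correlation r between visits; residual compliance SD is s; the true effect is zero.

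*Whole-trial average compliance, two visits:* slope = [37.5 × (1 + r)/2] / [(2s² + 25)/4].
- s = 20, r = 0.3: 24.375 / 206.25 = 0.118, or 1.18 per 10 points.
- s = 15, r = 0.5: 28.125 / 118.75 = 0.237, or 2.37 per 10 points.

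Simulation gave 1.19 to 2.38.

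*Whole-trial average, four visits, s = 15, r = 0.5 between all visits:*
- Mean covariance: (5 × 15/4) × (2 + 2 + 2 + 1.5)/4 = 35.16.
- Variance: [4 × 225 + 25 × (3 + 6 × 0.5)]/16 = 65.63.
- Slope: 35.16 / 65.63 = 0.536, or 5.4 per 10 points.

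*Preceding-interval compliance, independence working correlation, k visits:* slope = 75r(k − 1) / [ks² + 25(k − 1)].
- k = 2, s = 20, r = 0.3: 22.5 / 825 = 0.027, or 0.27 per 10 points.
- k = 4, s = 15, r = 0.5: 112.5 / 975 = 0.115, or 1.15 per 10 points.

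With an exchangeable working correlation, simulation gave about zero at two visits. At three to four visits it gave about 0.1 to 0.4 when the true correlation was first-order autoregressive.

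Taking compliance before the outcome therefore lowers this bias (0 to about 1.2, against about 1.2 to 5.4) but does not reliably remove it.

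**The case against.** **It is one word.** The analysis is labelled secondary, no decision hangs on it, and testing for the effect of a variable is common regression idiom. The first paragraph is itself loose when it speaks of an effect on a between-group difference. This stands as a limit on weight. It does not remove the point, because the SAP has the weaker word available one paragraph later and does not use it here.

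**Covariates may help.** The baseline list may be meant for this model too, and pain may be intended as a covariate. The text allows both. Neither makes the coefficient causal in general, and pain is itself post-randomisation.

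**The numbers are built in.** The confounding was assumed, and the sign follows the assumed direction. This stands in full: the figures show that bias can occur, not what it would be here.

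**Stronger readings that the SAP does not support.** A reader might infer that a pain-adjusted arm coefficient will be reported as the treatment effect. The SAP does not say that pain is a covariate or that an arm coefficient from this model will be interpreted. A reader might also infer a fault from the silence on how compliance is recorded; that may stand in the protocol and is not a finding.

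**Conclusion.** The point holds as a minor one. As worded, the aim of the compliance analysis is a conclusion that a non-randomised, post-randomisation exposure cannot support without assumptions that the SAP does not state. This follows from the design and not from the illustrative figures. The SAP gives no basis for the size or sign of any bias, so it would be wrong to conclude that the compliance result will be inflated, or by how much. It would be equally wrong to extend the criticism to the primary result: the intention-to-treat comparison of VISA-P does not use compliance and is unaffected.

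**What to change.** In the second paragraph, replace the stated aim with: *to estimate, in an exploratory analysis, the association between compliance and VISA-P, with arm, visit and the listed baseline variables in the model; the compliance coefficient will not be read as a causal effect.*

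Where the recording allows, use compliance over the interval before each VISA-P measurement instead of a whole-trial average. Present this as lessening reverse causation, not as a cure. The SAP does not say how often compliance is recorded, so feasibility has to be checked against the protocol.

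Optional: show results with and without experienced pain. If pain is a covariate, do not read that model's arm coefficient as the treatment effect, because pain arises after randomisation and the SAP expects it to differ between programmes.

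Cost: SAP wording and little extra analysis, with no new data and no change to the primary analysis. The trial gives up the claim of a compliance effect, and residual confounding remains.

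### The SAP words the painDETECT predictor as presence of a neuropathic component; the score itself would be the more efficient main form if its relation to outcome is roughly linear

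*SAP*

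**What the plan says.** The third paragraph of the SAP (section Statistical analysis plan JUMPER-study) extends the GEE model to a prognostic question: "This GEE-model will also be used to determine the association between the following variables and the course of symptoms resulting from patellar tendinopathy". Two variables follow. The first is "the level of passive coping (measured with the Pain Coping Inventory"), the second "presence of a neuropathic pain component (measured with the painDETECT questionnaire"). The nouns differ: coping is named by its level, neuropathic pain by its presence.

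The SAP gives no painDETECT cut-off, no number of groups and no coding for either variable in the model. Its only explicit mention of dichotomising is in the next paragraph, for two outcomes analysed with Fisher's exact test: "return to desired sport and subjective patient satisfaction, which we will dichotomize".

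**The concern.** Presence is ordinarily a yes-or-no state, so a reader carrying out this plan would probably code the predictor as 0 or 1. A two-group variable treats everyone on the same side of the cut as identical, and differences in score within each side then contribute nothing. If those differences carry prognostic information, the association is estimated less precisely than the collected questionnaire allows, and increasingly so as the positive group gets smaller.

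What is at stake is the power and precision of one secondary association.

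**Working it through.** **Inputs from the SAP.** The wording of the predictor, the model (GEE) and the question (association with the course of symptoms). For this analysis the SAP gives no sample size, power, significance level, cut-off or prevalence, so there is no figure of its own to reproduce.

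**Assumptions.** The score is normally distributed, its effect on outcome is linear, and a share *p* of participants lies above the cut, with *p* varied from 5% to 50%. For power: two-sided alpha of 0.05 and 80% power when the continuous score is used.

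**Step 1: information kept.** With cut *c* = z(1−p) and φ the standard normal density, the efficiency of the two-group version relative to the score is

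E = φ(c)² / [p(1−p)].

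This is the squared correlation between the score and its 0/1 version. Two worked cases:

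- p = 0.50: c = 0, φ(c) = 0.3989, so E = 0.1592 / 0.25 = 0.637.
- p = 0.10: c = 1.2816, φ(c) = 0.1755, so E = 0.0308 / 0.09 = 0.342.

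**Step 2: power after the split.** Power = Φ[(1.960 + 0.842)·√E − 1.960]. At p = 0.20, E = 0.490 and √E = 0.700, so the argument is 2.802 × 0.700 − 1.960 ≈ 0.00 and power is about 50%.

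**Step 3: sample size needed to make up the loss.** The multiplier is 1/E.

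| Share positive (assumed) | Information kept, E | Power, if 80% with the score | Multiplier of N, 1/E |
|---|---|---|---|
| 50% | 64% | 61% | 1.57 |
| 30% | 58% | 57% | 1.74 |
| 20% | 49% | 50% | 2.04 |
| 10% | 34% | 37% | 2.92 |
| 5% | 22% | 26% | 4.47 |

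The first row is the best case: under this model no cut keeps more than a median split, so the loss is at least about 36%. The last rows depend most on normality in the tail.

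**Step 4: sensitivity to linearity.** If the true effect is a step located at the cut, the two-group variable is the correct form and the split loses little or nothing. E is symmetric in the two forms, so in that case it is the linear score that would be inefficient. The table therefore describes one plausible shape of effect.

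**The case against.** A reader might infer that the SAP definitely cuts painDETECT into two groups. The text does not establish that. No cut-off or 0/1 code is given, and *presence* may only name what the questionnaire is meant to detect. Where the authors plan a two-group split they say so and give the categories, as for return to sport and satisfaction, and nothing of the kind accompanies painDETECT. The protocol, which is not at hand, may define the scoring. This objection stands: two-group coding is the natural reading of the wording, not a stated fact.

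A reader might also infer that coping and neuropathic pain would be compared with unequal precision. This is not supported either. A level can be high or low as easily as continuous, and the SAP lists the two variables without planning any comparison between them.

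Two further objections have weight. If the question really is whether having a neuropathic component matters, a presence/absence contrast answers it directly and a slope per point answers something slightly different. And the efficiency figures are general: the SAP supplies none of their inputs, so they do not show that a null result in this trial would be due to coding.

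What these objections do not remove is the wording. On its ordinary meaning it points to the less efficient form whenever the effect is graded. If it was meant only to name the construct, it misleads on a point that the same edit would settle. The point does not rest on a missing scoring rule, which the protocol may supply, but on the term that the SAP uses.

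**Conclusion.** The point holds as a modest improvement to a secondary analysis. The plan's wording most naturally describes a two-group predictor built from a graded questionnaire. If that is how it is entered, and if the score is roughly normal and linearly related to outcome, the share of information kept runs from about 64% at best to about 34% with 10% positive. Which of these figures applies cannot be said, because no prevalence is given, and under a threshold effect the loss could be small. No error in the plan's arithmetic is involved, and the primary VISA-P comparison is unaffected.

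**What to change.** In the third paragraph, replace the presence wording by the painDETECT score, entered as a continuous variable and reported per fixed number of points, as the main form. Add presence or absence as a supporting analysis.

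The change is one phrase and uses data that the plan already calls for. The cost is that a slope per fixed number of points is less direct to read than a two-group contrast. Keeping that contrast as the supporting analysis meets this, and also gives some cover should the effect be closer to a threshold than to a line.

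### Leaving missing VISA-P scores out does not avoid the bias the SAP expects, and the only check depends on an undefined 5% and names no method

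*SAP*

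**What the plan says.** In the missing-data paragraph that closes the SAP section Statistical analysis plan JUMPER-study, the rule and its purpose are: "Missing data will not be imputed to avoid the introduction of biased estimates of treatment effect". The reason follows: "We chose this approach because it is likely that missing data will not occur at random". Two facts are offered in support, that "patients are not blinded to the allocated therapy" and that "one exercise program is expected to cause significantly more pain than the other exercise program". The paragraph then gives the only further step: "Therefore, only a sensitivity analysis will be performed if missing data is more than 5%, blinded for the allocated exercise therapy".

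For the primary VISA-P comparison the same section says "we will use the Generalized Estimating Equation (GEE) model", adjusted for five baseline variables. None of the five records pain or compliance during the trial. No weighting for missingness and no working correlation is stated. The statement "Participants will be analyzed by intention-to-treat" settles the arm in which a participant is analysed; it does not say what happens to scores that were never recorded.

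**The concern.** The step from mechanism to method does not follow. If missingness depends on scores nobody saw, an imputation model built on observed data can mislead. An unweighted GEE fitted to the same observed data is exposed to the same problem. It generally needs missingness that is completely at random given arm and the covariates. A well-chosen working correlation extends this to drop-out that follows earlier recorded scores, but not to drop-out that follows the unseen score, and the SAP itself calls random missingness unlikely.

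The SAP's two supporting facts also suggest that missingness may differ between arms, which is the form that can distort a treatment contrast. At or below the trigger nothing examines this. Above it, almost any analysis would satisfy the text. A reader would take the primary estimate as protected from bias by design when it is not.

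**Working it through.** The SAP states no SD, sample size, number of visits or drop-out rate, so there is no figure to reproduce. Every input below is an assumption chosen to show the order of magnitude.

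**1. Basic arithmetic.** At one visit, let m be the share missing in an arm and d the amount by which the observed mean exceeds the unobserved mean. The true mean is (1 − m) × observed + m × unobserved, so the observed mean is too high by m × d. The bias in the contrast is therefore mA·dA − mB·dB.

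- Drop-out unrelated to the score (d = 0 in both arms): bias 0, however unequal the shares.
- 10% v 0%, d = 0.5 SD: 0.10 × 0.5 = 0.05 SD; with SD 15, 0.75 points.
- 20% v 5%, d = 1.0 SD in both arms: (0.20 − 0.05) × 1.0 = 0.15 SD, or 2.25 points.

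**2. Does the GEE remove this?** Simulation with true difference 0, correlation 0.5, three visits and the last visit subject to loss. Shifts are measured from the same data without losses (a complete-data estimate of −0.028 SD) and multiplied by 15.

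| Missing, A v B | Loss driven by | Independence GEE | Exchangeable GEE |
|---|---|---|---|
| 9% v 4% | unseen score | 0.018 + 0.028 = 0.046 SD (0.7 points) | 0.005 + 0.028 = 0.033 SD (0.5) |
| 27% v 9% | unseen score | 0.118 + 0.028 = 0.146 SD (2.2) | 0.068 + 0.028 = 0.096 SD (1.4) |
| 27% v 9% | previous seen score | 0.045 + 0.028 = 0.073 SD (1.1) | −0.026 + 0.028 = 0.002 SD (0.0) |

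The exchangeable structure deals with drop-out that follows a seen score and only reduces the bias when it follows the unseen one. Independence, which the SAP does not exclude, fails in both cases. The bias favours the arm with more missing data when patients doing badly leave, and reverses when patients doing well leave.

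**3. Size by missing share, and whether the 5% rule would fire.** Favourable case: exchangeable GEE with baseline as an outcome, SD 15, visit correlation 0.5 and 0.7, three follow-ups, monotone drop-out on the unseen current score, log-odds slopes per SD in the two arms of 0.7/0, 0.7/0.7 and 1.2/0, Monte Carlo error at most 0.02. For the trigger, loss is taken as linear up to x at the last of k follow-ups. The mean over follow-up scores is then x(k + 1)/(2k), which is 0.667x for k = 3, and the mean over all scheduled scores including baseline is x/2.

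| Missing at last visit | Bias, points | Overall: last visit | Overall: follow-up scores | Overall: with baseline |
|---|---|---|---|---|
| 25% v 13% | 0.3–1.6 | 19% | 12.7% | 9.5% |
| 20% v 0% | 0.5–1.3 | 10% | 6.7% | 5.0% |
| 15% v 5% | 0.3–0.9 | 10% | 6.7% | 5.0% |
| 12% v 6% | 0.2–0.7 | 9% | 6.0% | 4.5% |
| 10% v 0% | 0.3–0.6 | 5% | 3.3% | 2.5% |
| 7% v 3% | 0.1–0.4 | 5% | 3.3% | 2.5% |
| 4.9% v 4.9% | 0.0–0.3 | 4.9% | 3.3% | 2.45% |

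A separate run of the same set-up gave 0.29–1.53 for 25% v 13% and 0.26–0.61 for 10% v 0%. The last row shows that equal shares do not guarantee zero bias if drop-out depends on the score differently in the two arms.

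**4. What 5% can mean.** Setting each overall mean to 5%, the last-visit loss that just escapes is 5% if last-visit participants are counted. If follow-up scores are counted it is 10k/(k + 1)% = 6.7, 7.5, 8.0 and 8.3% for k = 2 to 5. With baseline included it is 10%. At 1:1 allocation the worst split that escapes therefore runs from about 10% v 0% to about 20% v 0%. A 10-point shift in the missing scores of the affected arm then moves the contrast by 0.10 × 10 = 1.0 to 0.20 × 10 = 2.0 points.

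With an assumed 40 per arm and three visits, 8 participants each missing one visit (7 v 1) is 8/80 = 10% of participants but 8/240 = 3.3% of visits, at 17.5% v 2.5% by arm. Four missing, all in one arm, is 4/80 = 5%, which is not above 5%, although that arm has lost 10%.

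**5. Scale.** Complete data, SD 15 and 40 per arm give an unadjusted standard error of 15 × √(2/40) = 3.35 points. The largest bias in step 3 is 1.6/3.35 = 0.48 of it; the largest at or below 5% at the last visit is 0.6/3.35 = 0.18.

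**The case against.** The strongest reply is a narrow reading: the SAP says only that imputation would introduce bias, and nowhere that the observed-data GEE is free of it. That is right about ordinary imputation. It still gives no reason to prefer the GEE, which the same mechanism biases, and it leaves the expected mechanism without any treatment in the primary analysis.

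Second, the sizes rest wholly on assumptions, and the larger ones do not escape the trigger. This stands in part. At 25% v 13% the check runs under all three overall readings. The 20% v 0%, 15% v 5% and 12% v 6% splits escape only if baseline scores count; the first two sit on the boundary, since their simulated overall shares of 5.1% and 5.05% would just trigger it. The 10-point shift is also larger than the simulated mechanism implies: 0.26/0.10 to 1.29/0.20 gives a gap of about 2.6 to 6.5 points. When the check does run, however, the SAP still does not say what it is.

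Third, blinding to allocation limits choosing a method to favour a known arm. With coded arms that is a real protection and harmless. Nothing in the text shows that pooled arms or one common shift is meant. If it were, the check could not see a between-arm effect: at 5% v 5% a common 10-point shift moves the contrast by 0.05 × 10 − 0.05 × 10 = 0, while a shift in one arm moves it by 0.5.

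Fourth, the protocol, which was not available, might give a method or a denominator. It could not repair the stated rationale.

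**Conclusion.** The concern holds, and the text is wrong as written. Avoiding bias is not a valid reason for an unweighted observed-data GEE under the mechanism the SAP expects, and the one safeguard is conditional on a loosely fixed threshold and has no stated content. Confidence is high for the logic and low for the size. On the assumptions above, bias ranges from nil to about 1.6 points with an exchangeable GEE at up to 25% v 13% missing, can be larger with an independence structure or heavier loss, and is modest near the trigger. Its direction cannot be derived from the SAP. If the SAP means only that more patients will leave one arm for reasons unrelated to their score, the bias is about 0, and it should say so. This should be corrected before analysis, but it does not undermine the primary model.

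**What to change.** 1. Delete the clause claiming that not imputing avoids biased effect estimates. Limit the no-imputation rule to the primary analysis, and state the missingness assumption under which the primary GEE is valid. Say whether the feared mechanism depends on the unseen score or only on arm.
2. Replace the 5% rule with a prespecified delta-adjusted (tipping-point) analysis of the primary VISA-P contrast, run whatever the missing percentage. Impute by arm from observed VISA-P scores, then add a shift varied independently in each arm over a grid fixed in advance. For example, −20 to +20 in steps of 5 gives 9 × 9 = 81 cells; these limits are illustrative and not derived from the SAP. Report where the conclusion changes. Code the arms A and B, and say that this is what blinding means here.
3. Optionally, as supportive only, add multiple imputation by arm or an inverse-probability-weighted GEE using earlier VISA-P scores, and pain and compliance where recorded before drop-out.

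The cost is SAP wording and modest programming, with no new data or patients. The primary estimate and its standard error are unchanged. The drawback is that the grid gives a range and not one corrected answer, and the statement on robustness may be less favourable.
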